A proposed randomized clinical trial of the effectiveness of a new breastfeeding- supportive texting program designed specifically for African-American/Black expectant women, as compared to a national maternal health texting program, on rates of exclusive breastfeeding at 2months; Short title: TOPS – Texting to Promote Breastfeeding).

XXXXXXXXXXXXXX

NCT06375655

01/19/2024

Objectives

Specific Aims

- 1. Demonstrate the feasibility and acceptability of a scaled-up program to deliver Team2BF text messages to AA/B expectant women considering breastfeeding.
- 2. Compare breastfeeding outcomes in the group receiving Team2BF with rates among those receiving Bright By Text.
- 3. Compare breastfeeding related knowledge and self-efficacy and social support as moderators of the relationship between the texting intervention and breastfeeding outcomes. (Exploratory aim)
- 4. Compare other key health outcomes (appointment attendance and vaccine receipt and book reading to infant) between the groups to verify that a focus on breastfeeding enhances rather than detracts from general maternal-infant health outcomes. (Exploratory aim)

Study Hypotheses

- Participants will find the Team2BF intervention acceptable as measured by >90%
 continuation, by >75% top score helpfulness of messages for breastfeeding and >75%
 endorsement of friend and family referral.
- 2. Participants receiving Team2BF will have significantly higher exclusive breastfeeding rates at 2 months as compared to participants receiving Bright By Text.
- 3. Breastfeeding knowledge, perceived social support for exclusive breastfeeding and self-efficacy will positively moderate the relationship between texting and breastfeeding outcomes, with those in the Team2BF group demonstrating a significantly greater increase in these domains with time as compared to the Bright By Text group.
- 4. Participants in both groups will have >75% rates of attendance among mothers at the (2-6 weeks) postpartum obstetrical visit and >75% rates of attendance and vaccine receipt for infants at the 2 month (6-12 weeks) well care visit.

Background

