For those who do not respond to the surveys, we will send one automated reminder text, and call up to 3 times, to make sure there are not technical difficulties. For those who STOP ALL or STOP SO MANY (to receive only one message per time point (by week prenatally or by day postpartum), we will ask, "Why unsubscribe?" If the participant does not respond, or does not respond to any of the surveys, we will call or email (two tries only) to understand why.

Mothers can continue to receive monthly messages for months 6-12 postpartum for TEAM2BF and up to 8 years postpartum for Bright By Text but this will not be incentivized.

Mothers will be asked to enter their delivery date; as a backup plan we are requesting to check both Delivery Logs (the PI receives these daily weekdays – they include all UHCMC MacDonald Women's deliveries) and the maternal EMR (electronic medical record) to make sure we do not miss this date if a mother forgets to enter her delivery date, since a different set of text messages is delivered postpartum and the postpartum surveys begin.

- 2- Research participants' safety and comfort will be protected by their ability to text "STOP" to end all messaging. Additionally in the informed consent we will have contact information for the study team, and the participant can call or email the study team with any concerns or questions.
- 3- Participants will use their own smartphones for the study. The smartphone is a device but it is not being studied. The text messages are being studied. Given the definition of software as a medical device (The term "Software as a Medical Device" (SaMD) is defined as software intended to be used for one or more medical purposes that perform these purposes without being part of a hardware medical device. Reference-https://www.fda.gov/medical-devices/digitalhealth-center-excellence/software-medical-

- device-samd), the text messaging does not appear to be SaMD because it is not being used to treat, diagnose or manage a condition or disease.
- 4- The source records for the study will be the survey data that participants provide and the electronic medical record.

Study Timeline

| Time point | Surveys | Approximate Time Needed | | | |
|-----------------|---|-------------------------|--|--|--|
| | | | | | |
| Enrollment | Demographics (your name, age, family | 7-10 minutes | | | |
| | supports, WIC status, other basic info) | | | | |
| | Infant Feeding Intentions Survey (4 | | | | |
| | questions) | | | | |

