| | Breastfeeding Knowledge Quiz (4 | | | | |
| | questions – answers follow) | | | | |
| | Breastfeeding Self-Efficacy Scale (14 | | | | |
| | items) | | | | |
| One week after | Infant Feeding Information-what milk is | 2 minutes | | | |
| delivery (PP) | baby drinking? | | | | |
| One month PP | Infant Feeding Information | 2 minutes | | | |
| Two months PP | Infant Feeding Information | 15 minutes | | | |
| | Breastfeeding Knowledge Quiz | | | | |
| | Breastfeeding Self-Efficacy Scale | | | | |
| | Breastfeeding Social Support Scale (16 | | | | |
| | items) | | | | |
| | Maternal Satisfaction (6 questions) | | | | |
| Three months PP | Infant Feeding Information | 3-4 minutes | | | |
| | Healthy Development (1 question) | | | | |
| | Maternal Satisfaction (6 questions) | | | | |
| Six months PP | Infant Feeding Information | 8-17 minutes | | | |
| | Healthy Development | | | | |
| | Maternal Satisfaction (6 questions) | | | | |
| | Study Thank you Survey | | | | |

Data to be Collected for your study

Outcome Measures

Aim #1 - Acceptability

Receipt of messages measures acceptability because participants can easily end messaging; if at least 90% of Team2BF participants continue receipt this will indicate acceptability of the intervention. This outcome will be enhanced by asking (a) a single 4 point Likert-scaled question

about the helpfulness of the texts for breastfeeding and (b) whether the participant would or would not refer a friend or family member to Team2BF.

Aim #2 – Breastfeeding Outcomes

The main outcome will be exclusive breastfeeding at 2 months because this is a meaningful milestone toward the public health goal of 6 months exclusive breastfeeding. We will assess partial and exclusive breastfeeding at hospital discharge and at 1, 2, 3 and 6 months post delivery using the World Health Organization definitions for exclusive and partial breastfeeding. We will also assess timing of discontinuation of breastfeeding if this occurs.

Aim #3 – Moderators of Breastfeeding Outcomes (Exploratory aim)

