By measuring breastfeeding knowledge at enrollment and again at 2 months we will assess for change in knowledge and for relationship to the main breastfeeding outcome. By measuring self-efficacy at enrollment and 2 months we will assess for changes in self-efficacy and relationship to the main breastfeeding outcome. We will assess perceived social support for exclusive breastfeeding at 2 months to compare those who did and did not achieve this goal.

Aim #4 – Non-breastfeeding Health Outcomes (Exploratory aim)

We will compare other key health outcomes between the groups that have been documented as relevant Bright By Text outcomes, as a direct Bright By Text outcome and a proxy to verify that a focus on breastfeeding enhances rather than detracts from general maternal-infant health outcomes. Attendance at the maternal postpartum check and attendance at the infant 2, 4 and 6 months well care appointments, including whether age-appropriate vaccines were received, will be assessed, as well as a measure of literacy (number of days per week reading books to baby).

Management of surveys – Generally participants will complete the enrollment timepoint surveys electronically, but if their phone is not able to photograph the QR codes that lead to the enrollment surveys, these will be administered on paper. The documents will be maintained on and transferred on the person of the study team member to the CCHP (Center for Child Health Policy) Office MCCO 650. The surveys will be kept in a locked cabinet with study team member access only, and after entry into REDCap will be retained until data analysis is complete.

Data Analysis Plan

Populations of each group will be compared using descriptive statistics (means and ranges, percents and frequencies). The main outcome of breastfeeding exclusively at 2 months will be compared between the two arms (texting groups) controlling for factors known to impact breastfeeding rates, as well as site of enrollment.

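### Hypothesis 3 predicts a greater increase in perceived social support with Team2BF, but the scale is given only at 2 months, so no increase can be computed for that domain

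*Combined protocol and SAP*

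**What the plan says.** All references are to the combined protocol and SAP.

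- **Specific Aims, 3** (exploratory) sets out to compare knowledge, self-efficacy and social support "as moderators of the relationship between the texting intervention and breastfeeding outcomes".
- **Study Hypotheses, 3** lists the same three domains. It ends its first statement with "self-efficacy will positively moderate the relationship between texting and breastfeeding outcomes" and then predicts their course by arm: "with those in the Team2BF group demonstrating a significantly greater increase in these domains with time as compared to the Bright By Text group".
- **Study Timeline** places the knowledge quiz and the self-efficacy scale at enrolment and at two months postpartum. The "Breastfeeding Social Support Scale" (16 items) appears only in the two-month row. The enrolment row has a demographics item, "Demographics (your name, age, family" and so on, which touches on supports but is not this scale.
- **Outcome Measures, Aim #3** agrees with the timeline. For knowledge: "By measuring breastfeeding knowledge at enrollment and again at 2 months we will assess for change in knowledge". For self-efficacy: "By measuring self-efficacy at enrollment and 2 months we will assess for changes in self-efficacy and relationship to the main breastfeeding outcome". For social support: "We will assess perceived social support for exclusive breastfeeding at 2 months to compare those who did and did not achieve this goal".
- **Data Analysis Plan** names arm comparisons for exclusive breastfeeding at 2 months and for timing of cessation, and none for the three Aim 3 domains.

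**The concern.** An increase needs two measurements on the same scale, and social support has one. A team that followed the plan exactly would reach the end of the study unable to evaluate Hypothesis 3 for that domain as it is written.

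The analysis text does not fill the gap. The one comparison it names for social support divides women by feeding outcome, not by randomised arm. It uses a score and an outcome recorded at the same 2-month point, so an association could arise because support helped feeding, because successful feeding coloured the report of support, or because of something behind both.

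The label is a related problem. A moderator is a characteristic, fixed before treatment can act, across whose levels the treatment effect differs. Hypothesis 3 calls the domains moderators and in the same sentence predicts that the intervention will raise them. A 2-month score that the texts have changed is an intermediate outcome. Unless the two roles are separated, the reader cannot tell which analysis Aim 3 intends.

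**Working it through.** **Step 1: schedule against hypothesis.** The plan gives no figure to reproduce here; the check is a count of scheduled administrations.

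| Domain | Enrolment | 2 months | Times measured | Increase computable? | Arm comparison in Aim #3 outcome text | Enrolment value usable as moderator? |
|---|---|---|---|---|---|---|
| Knowledge | yes | yes | 2 | yes | none stated | yes |
| Self-efficacy | yes | yes | 2 | yes | none stated | yes |
| Social support | no | yes | 1 | no | none stated; by feeding outcome only | no |

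The timeline table and the Aim #3 prose agree on the single time point, so this is not an artefact of a broken table. The demographics item at enrolment cannot serve as a baseline, because a change score needs the same instrument twice.

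**Step 2: what can still be estimated for social support.** Let Y0 be the score that would have been seen at enrolment and Y1 the 2-month score, with T for Team2BF and C for Bright By Text. Randomisation makes the expected Y0 equal in the two arms, so

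E[(Y1 − Y0) in T] − E[(Y1 − Y0) in C] = E[Y1 in T] − E[Y1 in C].

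The arm difference in 2-month scores therefore estimates the same effect as the arm difference in increase. It cannot show whether support rose at all: a higher Team2BF score at 2 months is equally compatible with a larger rise or a smaller fall.

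**Step 3: precision of that comparison.** Input: 36 per arm, the completer count in the sample-size paragraph of the Data Analysis Plan, taken as it stands. Degrees of freedom: 36 + 36 − 2 = 70.

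95% CI half-width = t(0.975, 70) × √(2/36) = 1.994 × 0.2357 = 0.470 SD.

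This assumes that all 36 per arm return the 2-month survey. Women who deliver before 36 weeks leave the study, and the protocol foresees survey non-response, so the interval could be wider.

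**Step 4: what a baseline buys in the other two domains.** Adjusting for the enrolment score multiplies the residual variance by 1 − r², where r is the correlation between enrolment and 2-month scores. The documents give no r, so a range is assumed. With 69 df, the half-width is about 0.470 × √(1 − r²):

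- r = 0.3: 0.449 SD
- r = 0.5: 0.407 SD
- r = 0.7: 0.336 SD

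The missing baseline therefore costs social support some precision but does not prevent an arm comparison.

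**The case against.** The strongest reply is that little is lost. Aim 3 is labelled exploratory, the arms are randomised, and the 2-month comparison of arms is available and estimates the same effect (Step 2). All of that stands, and it sets the severity. It does not repair the plan, which neither states that comparison nor limits its prediction to a difference at 2 months.

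Some stronger readings are tempting and should not be adopted.

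- *The plan has no arm comparison for social support anywhere.* A reader of the Aim #3 outcome text might infer this, but Hypothesis 3 does state an arm contrast that includes social support. What is missing is the data for that contrast in this domain. The silence of the Aim #3 outcome text about arms applies to all three domains.
- *The comparison by feeding outcome is offered as proof that the texts work.* The documents do not say so. They give its purpose as comparing women who did and did not reach the goal, and as a descriptive association it is legitimate.
- *The plan makes an unsupported mediation claim.* It makes none. It speaks of moderators and of a relationship to the main outcome.
- *Chance imbalance in unmeasured starting support is a further defect.* That variability is already inside the 0.47 SD half-width, and counting it again would be double counting.

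One could also keep the hypothesis and add the scale at enrolment. That is a fair alternative, but it lengthens the enrolment survey and gives no baseline for any woman already enrolled.

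**Conclusion.** The point holds as a mismatch between hypothesis, schedule and stated analysis. One of the three domains in Hypothesis 3 cannot be tested as worded, and this follows from the schedule alone, whatever the sample size. Two further gaps go with it: the Aim #3 outcome text states no arm comparison for any of the three domains, and the moderator label is applied to scores that the intervention is predicted to change.

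The documents do not support saying that an effect of the texts on social support is untestable. A randomised comparison of 2-month scores is available, with a half-width of about 0.47 SD under the assumption of 36 respondents per arm.

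Severity is minor. The aim is exploratory, the primary outcome of exclusive breastfeeding at 2 months is unaffected, and no data needed for the corrected analysis would be lost.

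**What to change.** 1. **Social support.** In Hypothesis 3 and the Aim #3 outcome text, replace the predicted increase with a between-arm difference in the 2-month score, reported as a mean difference with a 95% CI. Keep the comparison by feeding outcome, labelled as a descriptive association.
2. **Knowledge and self-efficacy.** State the analysis as the between-arm difference in 2-month score adjusted for enrolment score, with a 95% CI.
3. **Terminology.** Use *moderator* only for enrolment knowledge and enrolment self-efficacy, examined descriptively through an arm-by-baseline interaction. In Specific Aim 3, Hypothesis 3 and the Aim #3 heading, call the 2-month scores intermediate outcomes.

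Cost: edits to the aims, hypotheses and outcome sections, and one stated model. No survey, visit or participant is added. The price is a more modest claim: for social support, a difference at 2 months instead of an increase, with no baseline adjustment and no moderation analysis.

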In this research, we follow up on prior work that assessed the feasibility and acceptability and content of a culturally-tuned Breastfeeding-supportive Text Messaging Library intended for AA/B women. That work (TEAM2BF, STUDY20221270) demonstrated that expectant and delivered AA/B women found the text messaging process and content acceptable and helpful. None stopped any or all of the messaging, and approximately 6 messages were revised as recommended by participants. In this current study we aim to obtain preliminary efficacy data by comparing this texting library aimed at promoting breastfeeding to a professionally endorsed national maternal child health texting program, Bright By Text, whose focus is not breastfeeding. By comparing the TEAM2BF texting program to Bright By Text, we can compare whether message content impacts breastfeeding initiation and exclusivity at 2 months. The study design is equitable for participants in that both programs use a similar approach (texting), both are designed to be accessible to minoritized women of low socioeconomic status, and the comparator (Bright By Text) has demonstrated benefits.[16] This study aims to address identified gaps in breastfeeding support for AA/B women that we hope can ultimately reduce racial inequities in breastfeeding rates.

Inclusion and Exclusion Criteria

| | | Inclusion Criteria - mothers |
|--|--|---|
| 1. Expectant women initiating obstetrical care <34 weeks or at any | | Expectant women initiating obstetrical care <34 weeks or at any prenatal visit up |
| | | to 34 weeks gestation |

| 2. | Daily access to a mobile phone with text message capabilities, |
|----|--|
| 3. | 18 years or older (i.e., adult), |
| 4. | Self-identify as African-American/Black, |
| 5. | English speaking, and |
| 6. | Infant feeding plan of "might or will breastfeed". |
| 7. | Receive care at Ahuja Midtown or MAC1200 |

| | Exclusion Criteria |
|--|--------------------------------------|
| 1. | Minors |
| 2. Committed to feeding formula only to their infant | |
| 3. | No mobile phone with text capability |

| | Inclusion Criteria - infants |
|----|--------------------------------|
| 1. | Infant of maternal participant |

| | Exclusion Criteria -infants | |
|----|---------------------------------------|--|
| 1. | 1. Not infant of maternal participant | |

Number of Research Participants

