The study intervention is texting of health information from 28 weeks gestation or from time of enrollment (24-34 weeks) through one year postnatally. Participants will be block randomized to either Bright By Text or Team2BF. Blocks will be by CenteringPregnancy group for those in this program and in sequential blocks of the same number of participants for those in individual obstetrical care.

Those randomized to Bright By Text begin receiving texts as soon as they sign up, and those randomized to Team2BF begin receiving texts at 28 weeks or at the time of enrollment if after 28 weeks.

Bright By Text sends messages total from the first trimester through eight years postpartum, with 2-4 messages per week about a wide range of maternal and child health topics as outlined on their website; there are in total 8 messages about breastfeeding from the prenatal period to 4 months postpartum. Team 2BF includes 3-4 breastfeeding-supportive messages per time

interval, sent weekly from 28 weeks gestation through delivery, daily through 2 weeks postpartum, weekly from 2 to 10 weeks, and then monthly to one year. Other maternal health topics are not addressed.

We are not able to collect user interactions with the SMS system (were texts read or not, was message link clicked or not) within the TEAM2BF REDCap/Twilio system; Bright By Text does have ability to collect user interactions but there is no plan to collect this information for the research and no ability for the study team to receive or access it. For TEAM2BF, participants can text STOP ALL or STOP SO MANY (to receive only one message per time point [by week prenatally or by day postpartum]) and for Bright By Text, participants can text STOP at any time to discontinue receiving texts. At the point of any unsubscribe, and at the 6 months postpartum time point, the participant will be invited by text to participate in a 10-15 minute interview about their experience The interview will be audio recorded and the transcript destroyed once call notes are verified against the recording.

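### Exploratory Aim 4 promises a between-arm comparison, but Hypothesis 4 only asks each arm to exceed 75%, which tracks level and not difference

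*Combined protocol and SAP*

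**What the plan says.** Specific Aim 4, labelled exploratory, is comparative: "Compare other key health outcomes (appointment attendance and vaccine receipt and book reading to infant) between the groups to verify" that the breastfeeding focus helps and does not harm general maternal and infant health. The Aim #4 paragraph under Outcome Measures repeats this: "We will compare other key health outcomes between the groups that have been documented as relevant Bright By Text outcomes", partly as a proxy to "verify that a focus on breastfeeding enhances rather than detracts from general maternal-infant health outcomes". It lists the maternal postpartum check, "attendance at the infant 2, 4 and 6 months well care appointments, including whether age-appropriate vaccines were received", and the number of days per week of reading to the baby.

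Hypothesis 4 is the only place where a criterion is attached to these outcomes: "Participants in both groups will have >75% rates of attendance among mothers at the (2-6 weeks) postpartum obstetrical visit", and likewise above 75% for infant attendance and vaccine receipt at the 2-month visit. It gives no threshold for the 4- and 6-month visits or for book reading. Hypotheses 2 and 3, by contrast, each set Team2BF explicitly against Bright By Text.

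The Data Analysis Plan provides a descriptive comparison of the two groups' populations, an adjusted between-arm comparison of exclusive breastfeeding at 2 months, and a between-arm comparison of the timing of breastfeeding cessation. It gives no effect measure, interval or test for any Aim 4 outcome.

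**The concern.** The aim asks a question about a difference, and the hypothesis answers one about two separate levels. The difference matters because the programs differ in this very content. Of Team2BF the protocol says "Other maternal health topics are not addressed", while it says that "the comparator (Bright By Text) has demonstrated benefits". Whether replacing one program with the other costs anything in visits, vaccines or reading can only be read from the contrast between arms.

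As written, a report could state that Hypothesis 4 was met and be taken as showing that Team2BF does not detract, without the difference or its uncertainty appearing. The confirmatory word verify invites that reading.

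**Working it through.** **Inputs.** The Data Analysis Plan gives 36 dyads per group after attrition and 40 enrolled (36/0.90 = 40). That size was derived for exclusive breastfeeding; the plan gives no sample size, margin or expected rate for Aim 4, so there is no Aim 4 figure to reproduce. The attendance and vaccine rates below are assumptions.

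**What the rule requires.** Above 75% of 36 means more than 27, so at least 28/36 (77.8%) in each arm. The largest gap compatible with a pass is 36/36 − 28/36 = 22.2 points.

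**Passing tables with a significant Team2BF deficit** (two-sided Fisher p<0.05). There are only four, Bright By Text first:
- 36 v 28, p=0.005 (Newcombe 95% CI for the gap 8 to 38 points)
- 36 v 29, p=0.011
- 36 v 30, p=0.025
- 35 v 28, p=0.028

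At 34 v 28, p=0.085. A significant deficit alongside a pass therefore needs a comparator at or near the ceiling.

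**Probability of passing one measure.** With independent arms, P(pass) = P(X_B ≥ 28) × P(X_T ≥ 28), each X binomial with n=36. The single-arm probabilities are 0.072, 0.204, 0.436, 0.716, 0.920, 0.992 and about 1.000 at true rates of 65, 70, 75, 80, 85, 90 and 95%.

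| Bright By Text | Team2BF | P(pass) | P(pass and significant deficit) |
|---|---|---|---|
| 95% | 80% | 0.72 | 0.12 |
| 90% | 80% | 0.71 | 0.024 |
| 85% | 80% | 0.66 | 0.004 |
| 80% | 80% | 0.51 | 0.001 |

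Reading up this table, the deficit grows because the comparator improves, and the pass rate does not fall. The opposite direction must be shown too. With Bright By Text held at 90%:

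| Team2BF | 90% | 85% | 80% | 75% | 70% | 65% |
|---|---|---|---|---|---|---|
| P(pass) | 0.985 | 0.91 | 0.71 | 0.43 | 0.20 | 0.07 |

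Here the rule falls steeply. It responds to a low level in either arm. With equal arms it passes 51% of the time at 80% in both and 4% at 70% in both, so a failure does not show that Team2BF detracts either.

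Hypothesis 4 names three measures. Meeting all three cannot be more likely than meeting any one, so these pass rates are upper bounds for the whole hypothesis.

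**Precision of the contrast.** The 95% half-width is 1.96 × √(2p(1−p)/36): 18.5 points at p=0.80, 16.5 at 0.85 and 13.9 at 0.90. Identical results of 30/36 in both arms leave a Newcombe interval of about −18 to +18 points. For book reading the half-width is t(0.975, 70) × √(2/36) = 0.47 SD, or 0.7 to 1.2 days per week if the SD is 1.5 to 2.5 (assumed).

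**With all 40 per arm** (at least 31/40 in each), 95 v 80 passes 73% of the time, and 19% of the time with a significant deficit; 90 v 80 gives 73% and 4.8%. Half-widths are 13.1 to 17.5 points at rates of 90% to 80%. The picture does not change.

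**The case against.** Hypothesis 4 is a prediction, not a decision rule. No section says that meeting it settles Aim 4, and the aim already commits twice to a between-group comparison. A reader might infer that the 75% threshold replaces that comparison; the documents do not say so. This stands. What is left is that the promised comparison is nowhere specified, and that the only criterion written down for the aim is of another kind.

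A reader might also infer that a pass is unrelated to the difference between arms, or that it never becomes less likely as the deficit grows. That holds only when the deficit comes from a better comparator. With the comparator fixed at 90%, the pass rate drops from 98.5% to 7% as Team2BF falls from 90% to 65%, so the rule gives real protection against a low Team2BF rate.

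Third, a reader might treat the precision figures as a failure of power. The aim is exploratory, the protocol claims no power for it, it describes its efficacy data as preliminary, and it sizes the study on breastfeeding alone. The exploratory label excuses wide intervals. It does not excuse the word verify, or a criterion that does not measure what the aim asks.

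Finally, the most striking table needs a comparator at 100%, and every probability rests on assumed rates. Both points are fair and limit the weight of the finding.

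**Conclusion.** The point holds as a mismatch between aim and criterion, together with confirmatory wording. The above-75% rule describes the level in each arm and can be met with a moderate Team2BF deficit when the comparator rate is high: up to 22 points observed, and about 72% of the time on one measure at assumed true rates of 95% v 80%. It usually fails once Team2BF is well below 75%, and a pass alongside a statistically significant deficit is uncommon (12% at 95 v 80, 2.4% at 90 v 80). Neither a pass nor a non-significant difference would show that Team2BF does not detract, given half-widths of about 14 to 18 points at rates of 90% to 80%. The figures assume 36 per arm, independent observations and attendance rates that the documents do not supply. Severity is low: the aim is exploratory and the primary outcome is untouched. It is worth changing because the change is small.

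**What to change.** - Restate Hypothesis 4 as the Team2BF minus Bright By Text difference with a 95% CI for every Aim 4 outcome: risk differences for the postpartum visit, the 2-, 4- and 6-month infant visits and vaccine receipt, and a mean difference for days per week of book reading.
- Name the time point for book reading. The Study Timeline has a Healthy Development item at both 3 and 6 months, which appears to be the source.
- Add these contrasts to the Data Analysis Plan.
- Keep above 75% as a descriptive per-arm benchmark.
- Replace verify with estimate in Aim 4 and in the Aim #4 outcome paragraph.
- State that neither exceeding 75% in both arms nor a non-significant difference shows that Team2BF does not detract.

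This is wording only, with the same data and enrolment, and no margin is needed. The cost is that the likely Aim 4 conclusion becomes an imprecise estimate where the protocol now promises verification.
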